4.1.5.2. Regulatory aspects

Regulatory Authority approvals

Different Regulatory requirements and procedures persist between EU member states for clinical studies on the safety and performance of an IVD. As of July 2024, Greece and Germany do not have a centralized national

Regulatory Authority approval process in place and require notification concerning clinical studies after ethical approval has been obtained. Finland has recently established a national process with a 2-step approach: (1) ethical approval by the relevant local Ethics Committee, and (2) Finnish Medicines Agency (FIMEA) approval or notification, depending on whether the clinical study will involve a medical device (MD) or in vitro diagnostic medical device (IVD).

Regulatory assessments of the 2D-BioPAD device and Regulatory pathway

EVNIA has been leading the work on assessing the device type and classification and identifying the relevant regulatory pathways to facilitate preparing a regulatory-compliant clinical study protocol based on the current ethics-compliant protocol version 1.0. A T6.4 Regulatory Acceptability Plan template was prepared in M2 and has the objective to provide guidance on the regulatory pathway, requirements, and standards applicable for the 2D-BioPAD device. A meeting was held the 9th of July 2024 to discuss the 2D-BioPAD device classification. A 1st draft was prepared of specification of the device (Table 3). Further assessment of the device type and classification will be performed by EVNIA with input from consortium partners. Based on this knowledge an update of the Regulatory Acceptability Plan will be made by EVNIA and will guide on the preparation of an updated regulatory-compliant clinical protocol (M24).

Table 3: 2D-BioPAD device specification

Intended use	2D-BioPAD is a blood based diagnostic aid, based on AD related biomarkers detection and quantification.
Intended population	Individuals in the AD continuum (preclinical, prodromal or dementia stage)
Intended user	Qualified healthcare professionals who, in combination with other diagnostic tools, assess individuals within the AD continuum.
Pathology	Alzheimer's Disease (AD)

4.1.6. Study registration

Study registration in a suitable public registry (e.g., clinicaltrials.gov or equivalent) will be done following final ethical approval at all centres, and regulatory approval/notification as applicable, before the start of the study (M24).

4.2. Retrospective study

The 2D-BioPAD retrospective study (M25-M36) will use existing plasma samples from the three clinical study centres in Finland, Germany, and Greece. Study design is summarised in Figure 3.

[figure not shown]

Figure 3. 2D-BioPAD clinical pilot study design for the retrospective stage

4.2.1. Blood samples and selection criteria

Existing samples will be used if they are maximum 10 years old, continuously stored in -70°C freezer since collection, and there is consent for use of the samples and related clinical data, including shipping/sharing within the EU.

Table 4. Inclusion and exclusion criteria for the retrospective study

Inclusion criteria	
Plasma samples	
 • Maximum 10 years old • Up to 2 ml available for 2D-BioPAD pilot study • Stored in -70°C freezer • Existing consent to re-use for research, including shipping within the EU
Sample-related clinical data	
 • Diagnosis AD dementia, MCI due to AD, or no dementia-related disease (control) in connection to the blood sample collection time • Available data on CSF biomarkers, cognitive tests (at least MMSE), comorbidities, and medications in connection to the diagnostic workup • Existing consent to re-use data for research, including sharing within the EU
Exclusion criteria	
Sample-related clinical data	
 • Diagnosis of dementia other than AD • Mixed dementia • MCI suspected due to non-AD causes, as per clinical judgement based on centre-specific standard assessments

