Currently available diagnostic techniques include magnetic resonance imaging (brain MRI), lumbar puncture (biomarkers in cerebrospinal fluid, CSF), amyloid and tau PET, FDG-PET, and neuropsychological assessment. The most reliable methods are either expensive or invasive, and most are used to confirm the AD diagnosis only in the presence of substantial symptoms. While neuropsychological tests can detect subtle cognitive impairment in early disease stages, they are inadequate for distinguishing between different

¹ <https://www.alz.org/media/documents/alzheimers-facts-and-figures.pdf>

² <https://www.alzheimer-europe.org/dementia/prevalence-dementia-europe>

³ Janssen F, Bardoutsos A, El Gewily S, De Beer J. Future life expectancy in Europe taking into account the impact of smoking, obesity, and alcohol. *Elife*. 2021;10:e66590. doi: 10.7554/eLife.66590

⁴ Kumar A, Singh A, Ekavali. A review on Alzheimer's disease pathophysiology and its management: an update. *Pharmacol Rep*. 2015;67(2):195-203. doi: 10.1016/j.pharep.2014.09.004

⁵ <https://www.alz.org/alzheimers-dementia/diagnosis/why-get-checked>

⁶ Gustavsson E, Raaschou P, Lärffars G, Sandman L, Juth N. Novel drug candidates targeting Alzheimer's disease: ethical challenges with identifying the relevant patient population. *J Med Ethics*. 2021;47(9):608-614. doi: 10.1136/medethics-2021-107304

neuropathologies. Additional challenges⁷ have also been identified, due to diagnostic uncertainty and associated risks for the patient, accompanied by significant delays and costs for both patients and their families, but also for the health systems⁸.

To date, clinically approved fluid biomarkers exist only for Alzheimer's disease (AD)^{9,10} and until recently they were only tested in CSF. Recent major breakthroughs in accurate blood-based AD biomarkers, particularly β -amyloid (A β) 42/40 ratio, phosphorylated (p)-tau217, neurofilament light chain (NfL, neurodegeneration marker), and glial fibrillary acidic protein (GFAP, early marker of A β -related reactive astrogliosis), have the potential to truly revolutionize AD diagnostics^{11,12}. The first AD blood biomarkers were validated in 2022 in clinical trials¹³. However, the problems of accessibility and costs have not yet been fully addressed, and implementation in clinical practice is still limited.

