3.1. Retrospective study

The retrospective stage focuses on technical validation of the 2D-BioPAD diagnostic aid in a laboratory environment based on existing plasma samples. The main objectives are to:

- Analyze a set of up to five plasma biomarkers that can effectively support accurate early diagnosis of AD e.g., amyloid accumulation ($A\beta_{40}$, $A\beta_{42}$, and the $A\beta_{40/42}$ ratio), tau phosphorylation (e.g., p-tau₂₁₇), neurodegeneration (NfL), or inflammation (e.g., GFAP).
- Evaluate and validate the performance of the 2D-BioPAD diagnostic aid against benchmarking equipment for the same plasma biomarkers (available at the UEF Brain Research Unit biomarker laboratory) and/or state-of-the-art equipment for CSF biomarkers (as available from routine assessments conducted at the clinical study centres), considering also other patient-related (e.g., demographics, AD disease stage, comorbidities) and sample-related parameters (e.g., temperature, thaw-freeze cycles, other processing conditions).

Results from the retrospective stage will be used to improve the diagnostic aid design and offered functionalities as appropriate.

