4.4. Evaluation and validation design

4.4.1. Retrospective study outcomes

Table 8. Overview of the retrospective study outcomes

Outcome type	Description
Primary	
Comparison of plasma biomarker values between 2D-BioPAD prototype and benchmarking equipment.
 
Sensitivity, specificity, positive and negative predictive values of blood biomarkers measured with the 2D-BioPAD prototype for identifying:
 
 AD-related pathology (e.g., β-amyloid, tau), as indicated by CSF biomarkers measured during routine assessments at the clinical study centres using state-of-the-art equipment and established cut-offs. AD diagnosis established as per centre-specific standard procedures.
Secondary	Assessing the potential impact of other parameters, e.g., demographics, comorbidities on the primary outcomes.

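### The retrospective primary outcome is named accuracy for AD diagnosis, but the sample contains only AD and disease-free controls, so it measures AD versus no disease, and its predictive values reflect the sampling ratio

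*Protocol*

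**What the plan says.** Protocol section 4.4.1 (Table 8) lists among the primary retrospective outcomes: "Sensitivity, specificity, positive and negative predictive values of blood biomarkers measured with the 2D-BioPAD prototype for identifying" two targets. One is AD-related pathology as shown by CSF; the other is "AD diagnosis established as per centre-specific standard procedures". Comparison of values with the benchmarking equipment is also primary.

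Section 4.2.1 (Table 4) admits three groups: "Diagnosis AD dementia, MCI due to AD, or no dementia-related disease (control) in connection to the blood sample collection time". It excludes "Diagnosis of dementia other than AD", "Mixed dementia" and "MCI suspected due to non-AD causes, as per clinical judgement based on centre-specific standard assessments".

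Section 4.2.3 gives the size as 60 existing samples, 20 per centre. It says that the stricter criteria serve a well-defined case-control design and that a smaller number is enough for initial technical validation. The split between cases and controls is not stated.

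Section 3.1 describes the stage as technical validation in a laboratory and adds: "Results from the retrospective stage will be used to improve the diagnostic aid design and offered functionalities as appropriate". NfL is among the candidate markers there, and section 1 describes it as a marker of neurodegeneration.

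The prospective study differs. Section 4.3.1 (Table 5) does not exclude other dementias, section 4.4.3 lists other dementia as a diagnostic group, and Table 9 makes accuracy for AD diagnosis primary there too.

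**The concern.** The named outcome is broader than the sample can support. Specificity for AD diagnosis will be read as the chance that a person without AD tests negative. In a memory clinic many such people are impaired for another reason, and the retrospective set contains none of them. A marker that rises in any neurodegenerative disease and one that rises only in AD could score the same.

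PPV and NPV have a second, separate problem. In a case-control set the share of cases is chosen by the investigators, so these two figures describe that choice and not any clinic population. This would hold even if other dementias were admitted.

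At stake is what may be concluded from a primary outcome. A reader could take the retrospective specificity, PPV and NPV as evidence that the device identifies AD among patients, when they show only that it separates AD from absence of disease.

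**Working it through.** **1. The sample.** 3 centres × 20 = 60, which matches section 4.2.3. No power or precision inputs are given for the 60, so there is no sample-size formula to check.

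**2. Who can be AD-negative.** Table 4 admits AD dementia, MCI due to AD and controls. Counting MCI due to AD as AD, the negatives are the controls only. Samples allowed from people impaired by another cause: 0 of 60. Reading AD diagnosis as AD dementia alone would move MCI due to AD to the negative side, but would still bring in no non-AD disease.

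**3. PPV and NPV against the case share.** Assumed, since the protocol gives no values: sensitivity Se = 0.85, specificity Sp = 0.90. With p the share of cases,

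PPV = Se·p / [Se·p + (1 − Sp)(1 − p)] and NPV = Sp(1 − p) / [Sp(1 − p) + (1 − Se)p].

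- p = 1/3 (20 of 60): PPV = 0.2833/0.3500 = 0.81; NPV = 0.6000/0.6500 = 0.92
- p = 1/2 (30 of 60): PPV = 0.4250/0.4750 = 0.89; NPV = 0.4500/0.5250 = 0.86
- p = 2/3 (40 of 60): PPV = 0.5667/0.6000 = 0.94; NPV = 0.3000/0.4000 = 0.75

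The device is identical in all three rows; only the unstated split changes.

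**4. Specificity when other dementias are present.** With f the share of other dementias among non-AD patients,

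Sp = (1 − f)·Sp(controls) + f·Sp(other dementias).

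Table 4 sets f = 0, so Sp(other dementias) cannot be estimated from these samples. Two ends of the range:

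- *Marker equally specific in other dementias.* Sp(other) = Sp(controls), so specificity does not change for any f.
- *Marker raised equally in AD and other dementias.* Assume normal distributions with equal variance, a shift of 1.5 SD, and a cut-off giving 80% sensitivity. The cut-off lies 1.5 − 0.84 = 0.66 SD above the control mean, so Sp(controls) = 74.5%. Other dementias exceed it as often as AD does, so Sp(other) = 20%.
  - f = 0.25: 0.75 × 74.5% + 0.25 × 20% = 60.9%
  - f = 0.50: 0.50 × 74.5% + 0.50 × 20% = 47.2%

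The shift, the cut-off and f are assumptions; the protocol gives none of them.

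**The case against.** The strongest reply is that the restriction is open and deliberate. Sections 3.1 and 4.2.3 call this stage technical validation with a case-control design, section 2 calls the pilot's information on clinical performance preliminary, and anyone who reads Table 4 knows who the comparators are. The prospective study of up to 300 patients admits other dementias and records dementia type, so the missing contrast is already planned. NfL is included openly as the neurodegeneration component, and section 1 ties GFAP to amyloid-related change.

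Most of this stands. The exclusions suit technical validation and nothing here asks to change them. But declaring a case-control design does not correct a primary outcome named as accuracy for AD diagnosis, and it is itself the reason why PPV and NPV cannot be taken at face value.

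A reader might go further and infer that the retrospective specificity will select markers or fix cut-offs, and that those choices would then fail in the clinic. The protocol does not support this. Section 3.1 says only that results will inform design and functionality as appropriate. Section 4.4.3 looks at different cut-offs without carrying any forward, and Table 6 already lists the prospective benchmark markers. Nor does an AD-versus-control contrast penalise AD-specific markers; it merely fails to tell them from non-specific ones.

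**Conclusion.** The point holds as a mismatch between a primary outcome and its sample. It is not a contradiction, a wrong figure or a design fault. As planned, retrospective specificity measures AD against no dementia-related disease, with 0 of 60 samples able to show a false positive in other neurodegeneration. PPV and NPV move from 0.81/0.92 to 0.94/0.75 with the case share alone, under the assumed sensitivity and specificity.

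The effect on specificity in a broader population is unknown from these data. It ranges from none to a fall from 74.5% to 60.9% or 47.2% in the illustration. That lower end is a worst case: it assumes equal elevation in AD and other dementias, with all remaining non-AD patients behaving like controls. It should not be read as a forecast.

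Two related limits follow from Table 4. The CSF-based accuracy in Table 8 comes from the same narrow spectrum, and leaving out mixed dementia narrows the case side as well, which may raise sensitivity.

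**What to change.** In Table 8:

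- Restate the second accuracy target as *discrimination of AD dementia/MCI due to AD from persons with no dementia-related disease*.
- Drop PPV and NPV from the retrospective outcomes, or compute them only at a stated prevalence.
- Add a note that the CSF-based accuracy shares the same restricted spectrum.

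State that specificity, PPV and NPV for AD diagnosis come from the prospective study. This relies on the Table 5 criteria being kept. Section 4.3.5.1 allows a shift towards a case-control design if devices are short, and the limit on PPV and NPV would then apply there too.

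Choosing markers or cut-offs by agreement with the benchmark would not be a remedy: a device NfL value can agree perfectly with benchmark NfL and be just as non-specific.

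The cost is wording and a narrower retrospective claim. No new samples and no change to Table 4 are needed.

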4.2.2. Data collection

The following patient data already collected during the standard diagnostic workup in connection to the plasma sampling time will be used: diagnosis (AD dementia, MCI, or control/no dementia-related disease), cognitive tests, comorbidities, medications, other blood biomarkers (e.g., kidney and liver function).

Samples will be shipped on dry ice to the technical partners (i.e., ICN2 and GRAPHEAL) using established services for biological specimen shipping. Timelines are shown in Section 4.5.

4.2.3. Risk analysis

The retrospective study does not involve significant risks. It will use a total of 60 already existing plasma samples (20 per centre). Samples are already stored on-site in appropriate conditions. A smaller number of samples is considered sufficient for initial technical validation purposes in a laboratory environment. Stricter selection criteria (Table 4) are applied to ensure a well-defined case-control design, and availability of all necessary data. All clinical study centres have extensive experience and established contacts with appropriate services for biological specimen shipping.

4.3. Prospective study

The prospective study will be conducted between M30-M48. Patients and HCPs will be recruited at the three centres in Finland, Germany, and Greece. Up to 300 patients (\approx 100 per centre) will be recruited from individuals referred to the study centres (or related memory clinics where applicable) for assessment of cognitive status as per centre-specific standard procedures. The research participants may have subjective cognitive complaints, MCI, or dementia diagnosis.

The HCPs can be nurses or physicians (neurologists, psychiatrists, or geriatricians) depending on centre-specific organisation of standard healthcare. Per centre at least 2 HCPs will be recruited. HCPs may have different levels of experience, from limited experience (e.g., residency or <3 years in the dementia field) to extensive experience (e.g., specialist or at least 3 years in the dementia field). At least one HCP at each centre should have more extensive experience.

4.3.1. Selection criteria

Table 5. Inclusion and exclusion criteria for the prospective study

Inclusion criteria	
Patients	
 • Age 50 years or older • Subjective cognitive complaints, MCI or dementia diagnosis, as per centre-specific standard assessment procedures • Ongoing assessment after first referral to the clinical study centre, or diagnostic procedures completed \leq3 months before the first 2D-BioPAD study visit • Ability to provide written informed consent
HCPs	
 • 18 years or older • Certified HCP (e.g., nurse, physician) • Actively involved in the centre-specific assessment process for dementia-related diseases
Exclusion criteria	
Patients	
 • Any health conditions that substantially affect communication and/or ability to participate in study procedures, as judged by the study nurse or physician • Impaired capacity to consent as per centre-specific standard assessment

4.3.2. Overall study design

This is a **multicentre prospective observational study**. HCPs will use the 2D-BioPAD diagnostic aid to measure AD blood biomarkers in individuals referred to the three study centres for assessment of suspected AD/dementia disease. 2D-BioPAD baseline visit activities will be conducted only after the informed consent form has been signed. The overall study design is summarised in Figure 4.

The 2D-BioPAD baseline visit will be conducted after centre-specific standard assessment procedures are completed and a diagnosis and treatment/care plan have been decided according to standard clinic procedures. The 2D-BioPAD baseline visit can be a separate visit or can be conducted at the end of an already scheduled standard clinic visit, depending on patient preference and study centre logistics. The aim is to reduce burden for patients and limit interference with routine clinical activities.

As validation of the biomarker measures from the 2D-BioPAD diagnostic aid will be done as part of this study, these biomarker results will not be used for diagnosis or to guide treatment plans. HCPs participating in the 2D-BioPAD clinical pilot study who are directly involved in the standard diagnostic work-up and decision-making for patients tested with the 2D-BioPAD diagnostic aid must not have access to the biomarker results before the diagnosis and treatment/care plan are decided (See also Section 4.1.5.1 Ethical aspects).

[figure not shown]

Figure 4. 2D-BioPAD clinical pilot study design for the prospective stage

4.3.2.1. Training on using the 2D-BioPAD Diagnostic Aid

Training workshops for HCPs

ICN2 will plan a training workshop for the HCPs in cooperation with the three study centres. The format will likely consist of virtual sessions, combining practical hands-on training with app-based tutorials. In-person session could be considered according to the needs of the HCPs and the availability of the trainers.

User guides and manuals

The mobile app will feature a comprehensive Digital User Guide that provides step-by-step instructions on device usage. This includes guidance on:

- Setting up the device.
- Procedure for collecting samples.
- Procedure for pre-processing samples.

- Using the device for testing.
- Accessing the results and safely disposing of consumables.

The guide will be available in both digital (within the app) and downloadable PDF formats, as well as through video tutorials and interactive elements embedded in the app for ease of use.

Handling technical issues and troubleshooting

For troubleshooting, there will be app-based support features for technical issues. The app will include common troubleshooting scenarios, and in case of more critical problems, HCPs will be able to directly contact the technical support team via phone or through the app's integrated support feature. The importance of real-time assistance will be carefully considered, particularly when samples are being processed.

4.3.3. Recruitment

All clinical study centres have well-established recruitment procedures for research studies, including both HCPs and patients. Recruitment timeline for the 2D-BioPAD clinical pilot study is shown in section 4.5. Continuous recruitment will be conducted until a total sample of ≈ 300 patients will be reached. Step 1 (feasibility test-run) will include the first 30 recruited patients (10 per study centre). In Step 2, recruitment will be scaled up to include 270 patients until the total $N \approx 300$ is reached.

4.3.3.1. Step 1: feasibility test-run

In Step 1, a small-scale feasibility test run will be performed with the first 30 recruited patients (10 per study centre) to refine the procedure for using the diagnostic aid by identifying constraints, limitations, and potential improvements. To assess the potential impact of fasting versus non-fasting state, and time of day, blood sampling for each patient will be done **in the morning** (one fasting sample before 09:00, and one sample about one hour after breakfast on-site) **and in the afternoon** (non-fasting after 13:00 on the same day). This is based on recent studies indicating that AD blood biomarker levels may be modified by food intake, and also showing significant changes over a 3-hour interval in the fasting control group²⁴.

4.3.3.2. Step 2: scaling up the clinical pilot study

In Step 2, the clinical pilot study will be scaled up with recruitment of the rest of the patients (up to a total of 300, 100 patients per centre for step 1 and step 2 together). Up to one year follow-up will be included for patients with inconclusive diagnosis following the initial assessment. The follow-up protocol will be according to centre-specific standard procedures.

